2.0 OBJECTIVES & ENDPOINTS

2.1 Primary Objective & Endpoint

To determine progression free survival (PFS) in patients with newly recurrent HER2 negative IBC treated with nivolumab and ipilimumab according to Response Evaluation Criteria in Solid Tumors (RECIST) v 1.1.⁴⁶

The time in months from start of treatment to progression or death will be measured for all patients who receive at least one dose of study drug. Patients will be followed up to 2 years after completion of treatment.

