4.0 TREATMENT PLAN

4.1 Overview

Nivolumab and ipilimumab combination will be administered intravenously until disease progression or intolerable toxicity. Nivolumab will be given at 240mg every 2 weeks for the first 16 weeks, and at 480mg every 4 weeks thereafter (starting with C2D29, 1 cycle = 12 weeks). Ipilimumab will be given at 1mg/Kg every 6 weeks over approximately 90 minutes. On days when both nivolumab and ipilimumab are administered, nivolumab should be given first, followed by ipilimumab about 30 minutes later. Scans will take place every 12 weeks for disease assessment. Note: Please refer to section 4.4 for patients who may continue treatment after initial progression.

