5.0 STUDY PROCEDURES

Day of each cycle	Screening ¹	On Treatment (1 cycle = 12 weeks) ^{12,13}																		Off Treatment		
		Cycle 1 (±3 days)							Cycle 2 (±3 days)							Cycle 3+ (±3 days)						
		1	15	29	43	57	71	1	15	29	43	57	71	1	15	29	43	57	71	End of Treatment ¹⁴	Follow -Up ¹⁵	
Weeks on study		1	3	5	7	9	11	13	15	17	19	21	23	25	27	29	31	33	35 +			
Assessment or Activity																						
Informed Consent	X																					
Medical history	X																					
Physical exam ²	X	X	X	X	X	X	X	X	X	X	X	X	X	X	X	X	X	X	X	X	X	
ECOG status	X	X	X	X	X	X	X	X	X	X	X	X	X	X	X	X	X	X	X	X	X	
ConMeds	X	X	X	X	X	X	X	X	X	X	X	X	X	X	X	X	X	X	X	X	X	
Adverse events	X	X	X	X	X	X	X	X	X	X	X	X	X	X	X	X	X	X	X	X	X ¹⁵	
Scans ³	X	X ³						X ³								X ³					X	
Lesion Photos ¹⁶	X	X						X								X					X	
CBC with diff ⁴	X	X	X	X	X	X	X	X	X	X	X	X	X	X	X	X	X	X	X	X	X	
Chemistry panel ⁵	X	X	X	X	X	X	X	X	X	X	X	X	X	X	X	X	X	X	X	X	X	
Amylase/Lipase	X	X ⁶						X ⁶								X ⁶					X	
TSH (free T4) ⁷	X	X ⁷						X ⁷								X ⁷						
Pregnancy test ⁸	X	X						X								X					X	
Nivolumab ⁹		T	T	T	T	T	T	T	T	F	F	F	F	F	F	F	F	F				
Ipilimumab ¹⁰		X		X		X		X		X		X		X		X		X				
Tissue collection ¹¹	X	X ¹¹																				
Survival status																					X	

T = 240mg nivolumab

F = 480mg nivolumab

¹ CBC with diff and Chemistry panel should be within 14 days of registration; all other screening procedures should take place within 28 days of registration unless specified otherwise.

² Includes vital signs (pulse, blood pressure), height and smoking history (baseline only) and weight.

³ Imaging must include Chest, Abdomen, and Pelvis as well as a bone scan. Scans may be by CT, PET/CT or MRI (per treating investigator's discretion) with contrast unless strictly contraindicated as well as a bone scan; the same modality used at baseline should be used

throughout. Tumor assessment should be done at screening, cycle 2 day 1 (\pm 1 week) and Day 1 of each cycle (every 12 weeks) thereafter, regardless of dosing schedule until progression or treatment discontinuation whichever occurs later. Tumor assessments will incorporate both RECIST and clinical criteria. Brain MRI is the preferred imaging method for evaluating CNS metastasis, and assessment is only required during screening for eligible subjects with symptomatic CNS involvement.

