6.0 ENDPOINT ASSESSMENT

6.1 Definitions

For the purposes of this study, patients should be re-evaluated for response every 12 weeks (± 1 week). In addition to a baseline scan, confirmatory scans should also be obtained 8 weeks following initial documentation of objective response greater than Stable Disease (SD). Tumor assessments for all subjects should continue as per protocol even if dosing is interrupted. Tumor measurements should be made by the same investigator or radiologist for each assessment whenever possible. Changes in tumor measurements and tumor responses to guide ongoing study treatment decisions will be assessed by the investigator using RECIST.

Response and progression will be evaluated in this study using the new international criteria proposed by the revised Response Evaluation Criteria in Solid Tumors (RECIST) guideline (version 1.1)⁴⁶. Changes in the largest diameter (unidimensional measurement) of the tumor lesions and the shortest diameter in the case of malignant lymph nodes are used in the RECIST criteria.

High resolution CT with oral/intravenous contrast or contrast-enhanced MRI is the preferred imaging modalities for assessing radiographic tumor response. If a subject has a known allergy to contrast material, please use local prophylaxis standards to obtain the assessment with contrast if at all possible, or use the alternate modality. In cases where contrast is strictly contraindicated, a non-contrast scan will suffice. Screening assessments should be performed within 28 days of registration. Brain MRI is the preferred imaging method for evaluating CNS metastasis, and assessment is required during screening in all eligible subjects. All known or suspected sites of disease (including CNS if history of CNS metastases) should be assessed at screening and at subsequent assessments using the same imaging method and technique. If more than one method is used at screening, then the most accurate method according to RECIST 1.1 should be used when recording data, and should again be used for all subsequent assessments. Previously treated CNS metastases are not considered measurable lesions for purposes of RECIST determined response. Subjects with a history of brain metastasis should have surveillance MRI approximately every 12 weeks, or sooner if clinically indicated.

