6.2 Primary Endpoint

Progression free survival defined as time in months from the date of first study treatment to the date of disease progression or death from any cause, whichever comes first. All patients who receive at least one dose of nivolumab/ipilimumab combination will be included in the primary analyses of PFS. The Response Evaluation Criteria in Solid Tumors (RECIST 1.1) criteria will be used for objective tumor response assessment (when disease is measurable and non-measurable).⁴⁶

- Patients with IBC often do not have measurable disease. For example, patients will sometimes have just recurrent skin involvement, pleural effusions, or bone disease. Measurable disease is not a requirement for enrollment on the study.
- For patients who have only non-measurable disease, unequivocal progression or response will be defined after consideration if the increase in overall disease burden based on the change in non-measurable disease is comparable in magnitude to the increase that would be required to declare PD or tumor response for measurable disease. Complete response will be defined as disappearance of non-measurable disease.
- Clinical and radiological assessments will be performed every 8 weeks (+- 7 days) while on treatment and patients will be followed for up to 2 years after completion of treatment.

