10.2 Sample Size and Accrual

We previously identified 44 patients who were included in a retrospective study of the prognostic significance of HER2 status in IBC. These patients had both HER2 negative and HER2 positive disease, developed metastases, and experienced a disease progression. The median time from the first progression of their metastatic disease to the second progression event or death was approximately 3 months. These patients will be considered our historical control group.

Nivolumab ipilimumab combination will be considered of interest for further study if the median PFS time is increased to at least 6 months. We will test the null hypothesis that median PFS is at most 3 months versus the alternative that it is at least 6 months. The null corresponds to 25% PFS at 6 months under the exponential distribution of PFS versus an alternative 6 month PFS rate of 50%. The null corresponds to 50% PFS at 3 months and the alternative corresponds to 70.71% PFS at 3 months under the same conditions.

We will initially recruit and treat 15 patients. If 7 or fewer initial cohort patients are progression free at 3 months the study will be terminated for lack of efficacy. If at least 8/15 are progression-free at 3 months then we will recruit an additional 14 patients for a total of 29.

The patients free of progression at 3 months from the initial cohort will remain on study until either progression or 6 months evaluation. Second cohort patients will be evaluated at 6 months only. If at least 11/29 patients are progression free at 6 months the null hypothesis will be rejected.

The chance of early study termination (3 months follow up with 15 patients) is 50% under the null and 4.4% under the alternative. Study power is 90% with overall type I error of 7%. The design follows: Early stopping designs based on progression-free survival at an early time point in the initial cohort.⁴⁹

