10.3 Data Analyses Plans

Response rates and 95% confidence intervals will be calculated using exact binomial probability distributions. Progression-free survival and overall survival will be analyzed using Kaplan-Meier curves. Adverse events will be summarized descriptively using frequencies and percentages. Statistics will be given on type, severity, frequency and attribution of adverse events. Sample size considerations are described above.

An intention to treat analysis will be done. In a single group Phase II study, intention to treat means that all patients who are evaluated and registered for the study are followed and analyzed regardless of (a) whether they were subsequently found to be protocol ineligible and (b) the amount of study treatment (nivolumab/ipilimumab) they received. To calculate progression-free and overall survival in patients who received nivolumab/ipilimumab, times will be taken from the time of study registration. This definition parallels the definition of intention to treat in randomized clinical trials.

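### The stated 7% type I error and 90% power hold for PFS status at exactly 3 and 6 months, but no deciding scan, month length or single start date fixes that status

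*Combined protocol and SAP*

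**What the plan says.** Section 10.2 assumes exponential PFS with a median of 3 months under the null and 6 months under the alternative. Progression-free rates are therefore 50% and 25% at 3 and 6 months under the null, and 70.71% and 50% under the alternative. The trial stops if 7 or fewer of the first 15 patients are progression free at 3 months. Otherwise 14 more are recruited, and "If at least 11/29 patients are progression free at 6 months the null hypothesis will be rejected". The 7%, 90%, 50% and 4.4% figures are repeated in the Study Summary. No scheduled assessment is tied to either landmark, and a month is not defined. The historical median behind the null is given only as approximately 3 months.

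The scan interval appears in two forms:
- Section 4.1: "Scans will take place every 12 weeks for disease assessment". Section 5.0, footnote 3: "Tumor assessment should be done at screening, cycle 2 day 1" (within a week either way), then day 1 of each 12-week cycle. Section 6.1: "patients should be re-evaluated for response every 12 weeks", again within a week. The Study Summary and section 2.2.1 also use 12 weeks.
- Section 6.2, which defines the primary endpoint: "Clinical and radiological assessments will be performed every 8 weeks (+- 7 days) while on treatment".

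The start of PFS also appears in two forms:
- Section 2.1: "The time in months from start of treatment to progression or death will be measured". Section 6.2: "time in months from the date of first study treatment to the date of disease progression".
- Section 10.3, for PFS and OS: "times will be taken from the time of study registration". Footnote 12 of section 5.0 allows up to 14 days between registration and first treatment.

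**The concern.** The rules of 8/15 and 11/29 were calibrated for status at exactly 3 and 6 months. Scans at weeks 12 and 24 from first dose come about 7 and 15 days before those points (91.3 - 84 and 182.6 - 168). A patient who progresses in that gap, and whose progression is not noticed clinically, counts as a success. Under the null this raises the chance of reaching 11 of 29.

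The conflicting interval and start date move the deciding scans further, in either direction. They also change the chance that an ineffective regimen is stopped at the interim. In a 29-patient single-arm trial the conclusion can turn on 10 versus 11 patients, so the rule for counting them should be fixed before the data are seen.

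**Working it through.** **Inputs.** From section 10.2: 15 + 14 patients, continue at 8 or more of 15, reject at 11 or more of 29, medians of 3 and 6 months, exponential PFS. From sections 5.0 and 6.1: scans at weeks 12 and 24, within a week. From section 6.2: scans every 8 weeks, within 7 days. From footnote 12 of section 5.0: a gap of 0 to 14 days. Assumption: a calendar month of 30.4375 days, so 3 months = 91.3 days and 6 months = 182.6 days.

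**Formulas.** With deciding days t3 and t6 and median m in months, p = 0.5^(t/30.4375/m).
- Early stopping = P(Bin(15, p3) ≤ 7).
- P(reject) = sum over k = 8 to 15 of P(Bin(15, p3) = k) × P(Bin(k, p6/p3) + Bin(14, p6) ≥ 11).

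**The plan's own figures.** Null, p3 = 0.5 and p6 = 0.25: the terms for k = 8 to 15 are 0.01638 + 0.01973 + 0.01714 + 0.01064 + 0.00461 + 0.00132 + 0.00023 + 0.00002 = 0.0701. Alternative, p3 = 0.7071 and p6 = 0.5: power 0.9013. Early stopping is 0.500 and 0.0437. All four stated figures reproduce, so section 10.2 has no arithmetic error.

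**On-schedule 12-week scans from first dose.** 84/30.4375 = 2.76 months and 168/30.4375 = 5.52 months. Null: p3 = 0.5285, p6 = 0.2794. Alternative: p3 = 0.7270, p6 = 0.5285. Type I error is 0.1350, power 0.9412, and early stopping 0.411 (null) and 0.029 (alternative).

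**Events detected between scan and landmark.** If a share q is caught clinically, p becomes p(scan) - q × [p(scan) - p(landmark)].
- q = 50%: null p3 = 0.5143, p6 = 0.2647; type I error 9.9%.
- q = 75%: null p3 = 0.5071, p6 = 0.2573; type I error 8.4%.
- q = 90%: null p3 = 0.5029, p6 = 0.2529; type I error 7.5%.

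**A 4-week month.** 84/28 = 3 and 168/28 = 6. If the historical median is read in the same unit, the result is again 7.0% and 90.1%.

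**Other readings, with nothing detected between scans.** The finding at the named scan is taken as the landmark status.

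| Reading | Days t3/t6 | Type I error | Power | Null early stopping |
|---|---|---|---|---|
| 12-week, first dose, both scans a week early | 77/161 | 18.4% | 95.9% | 33% |
| 12-week, first dose, both a week late | 91/175 | 9.7% | 91.8% | 50% |
| 12-week, registration 7 days before dose | 91/175 | 9.7% | 91.8% | 50% |
| 12-week, registration 14 days before dose | 98/182 | 6.8% | 89.0% | 58% |
| As above, both a week late | 105/189 | 4.7% | 85.7% | 65% |
| 8-week, week 8 decides the interim | 56/168 | 15.6% | 96.2% | 11% |
| As above, both a week early | 49/161 | 20.7% | 97.4% | 6% |
| 8-week, week 16 decides the interim | 112/168 | 9.8% | 87.4% | 72% |

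The table does not cover strict comparison of a progression date with the landmark. On the registration clock with a gap of 8 days or more, the week-12 scan falls on day 92 to 98. That is after day 91.3, so progression first seen there would be dated too late to count at 3 months.

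**The case against.** A reader might infer that the true type I error is 13.5% and the stated 7% is wrong. The documents do not support that, for three reasons.
- Section 6.2 already counts documented progression or death from any cause, whichever comes first. Section 5.0 schedules a physical examination at each visit and lets tumor assessment use clinical criteria. Some events between scan and landmark will be caught, and each one moves the figure towards 7%.
- Cycles and scans run in 12-week units, so a 4-week month is a natural reading, and under it the stated figures hold.
- The null median is only approximate. If it is really 12 weeks (2.76 calendar months), scans at weeks 12/24 give exactly 7.0%. Even at exact landmarks, null medians of 2.75 and 3.26 months give 3.0% and 13.5%. Uncertainty in the benchmark is as large as the timing effect.

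The 8-week interval stands in one bullet of section 6.2 against several statements of 12 weeks. Appendix E records a move to 12-week scans and does not list 6.2 among the affected sections, so the bullet is probably a leftover. Letting a week-8 scan (56/30.4375 = 1.84 months) decide 3-month status is a strained reading. The 18.4%, 20.7% and 4.7% figures need every patient scanned at the edge of the window.

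A reader might also infer that the deciding scan would be picked after the results are known. Nothing in the documents shows such an intention, and section 11.8 requires committee-approved data for publication. That limits the risk but does not define the landmark.

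What stands: the current text gives two scan intervals and two start dates, and names no deciding assessment. On a calendar-month reading, on-schedule scans from first dose deliver the stated 7% only if essentially all events between scan and landmark are detected clinically.

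**Conclusion.** The point holds as a mismatch between the decision rule and the assessment schedule. The section 10.2 figures are right for status at exactly 3 and 6 months. For on-schedule 12-week scans from first dose, type I error is about 13.5% at the upper side, with power 94% and null early stopping 41%. That rests on exponential PFS, calendar months, a true 3.0-month null median and no detection between scans. Detection of half to 90% of intervening events gives about 10% to 7.5%. A 4-week month, applied to the historical median as well, gives 7.0%.

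Across the permitted windows, both start dates and both intervals, type I error runs from about 5% to 21%, taking the week-12/24 scans or their 8-week counterparts as the deciding ones. With 12-week scans timed from first dose, power stays above 90%, so the exposure there is to a false positive. It falls slightly below 90% on the registration clock with a 14-day gap, and when week 16 decides the interim.

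**What to change.** 1. Reconcile the scan interval in section 6.2 with sections 4.1, 5.0 and 6.1.
2. Reconcile the PFS start date in sections 2.1 and 6.2 with section 10.3.
3. In section 10.2, name the scheduled assessment and window that decide 3-month and 6-month status. Define a month in days or weeks, and apply the same unit to the historical median.
4. Keep 8/15 and 11/29. Recompute type I error, power and both early-stopping probabilities for that definition, and restate them in section 10.2 and the Study Summary if they change.

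The cost is wording in these sections and one recalculation, with no extra patients or scans and no new threshold. If a 4-week month is what was meant, one sentence saying so leaves the stated figures as they are once items 1 and 2 are settled on 12-week scans timed from first dose. The downside is that the restated type I error may be less favourable than 7%.

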10.3 Data Analyses Plans

Response rates and 95% confidence intervals will be calculated using exact binomial probability distributions. Progression-free survival and overall survival will be analyzed using Kaplan-Meier curves. Adverse events will be summarized descriptively using frequencies and percentages. Statistics will be given on type, severity, frequency and attribution of adverse events. Sample size considerations are described above.

An intention to treat analysis will be done. In a single group Phase II study, intention to treat means that all patients who are evaluated and registered for the study are followed and analyzed regardless of (a) whether they were subsequently found to be protocol ineligible and (b) the amount of study treatment (nivolumab/ipilimumab) they received. To calculate progression-free and overall survival in patients who received nivolumab/ipilimumab, times will be taken from the time of study registration. This definition parallels the definition of intention to treat in randomized clinical trials.

11.0 STUDY MANAGEMENT

11.1 Institutional Review Board (IRB) Approval and Consent

It is expected that the IRB will have the proper representation and function in accordance with federally mandated regulations. The IRB should approve the consent form and protocol.

In obtaining and documenting informed consent, the investigator should comply with the applicable regulatory requirement(s), and should adhere to Good Clinical Practice (GCP) and to ethical principles that have their origin in the Declaration of Helsinki.

NU Study Number: NU 16B07
Other Study Number: CA 209-782

Before recruitment and enrollment onto this study, the patient will be given a full explanation of the study and will be given the opportunity to review the consent form. Each consent form must include all the relevant elements currently required by the FDA Regulations and local or state regulations. Once this essential information has been provided to the patient and the investigator is assured that the patient understands the implications of participating in the study, the patient will be asked to give consent to participate in the study by signing an IRB approved consent form.

Prior to a patient's participation in the trial, the written informed consent form should be signed and personally dated by the patient and by the person who conducted the informed consent discussion.

11.2 Amendments

The Principal Investigator will formally initiate all amendments to the protocol and/or informed consent. All amendments will be subject to the review and approval of the appropriate local, institutional, and governmental regulatory bodies, as well as by BMS. Amendments will be distributed by the lead institution (Northwestern) to all affiliate sites upon approval by the Northwestern University IRB.

11.3 Registration Procedures

Patients may not begin protocol treatment prior to registration. All patient registrations will be registered centrally through the Clinical Research Office at Northwestern University before enrollment to study. Please contact the assigned Quality Assurance Monitor (QAM) or email the QA Department ([contact]) for questions regarding patient registration.

Prior to registration, eligibility criteria must be confirmed by the assigned QAM. The study coordinator will screen all subjects for potential registration via the web-based application NOTIS (Northwestern Oncology Trial Information System), which is available at: <https://notis.nubic.northwestern.edu>. Please note that a username and password is required to use this program, and will be provided during site activation prior to training on the NOTIS system. Training on eCRF completion will be provided at the time of site activation.

BEFORE a patient can be treated on study, please complete and submit the following items to confirm eligibility and receive an identification number:

- Patient's signed and dated informed consent form (upload to NOTIS and keep original hard copy in a secure location/study chart)
- Eligibility checklist (signed and dated by the treating physician – upload to NOTIS)
- Eligibility eCRF (complete in NOTIS)
- Copy of the pathology report (upload to NOTIS)

The QAM will review the registration, register the patient, assign a subject identification number, and send a confirmation of registration to study personnel. Registration will then be complete and the patient may begin study treatment.

